6. STATISTICAL METHODS AND DETERMINATION OF SAMPLE SIZE

6.1 Statistical evaluation

Statistical analysis will be carried out by Biostatistics at AstraZeneca, Wilmington, Delaware using SAS (version 8). Summary graphics required for presentation in the text portion of the Clinical Study Report (CSR) will be done using Sigmaplot 2000. Other graphics intended for use as supplemental figures and individual profile figures will be done using SAS. A comprehensive Statistical Analysis Plan (SAP) will be prepared and finalized before unblinding and analysis of the data.

The goal of the PK analysis is to estimate the effect of ethnicity (Japanese vs. Caucasian) on exposure to AZD6140 and AR-C124910XX over the current dose range of AZD6140. Therefore, no formal hypothesis testing will be performed, though estimation of the ratio of exposure (Japanese/Caucasian) will be supported with two-sided 90% confidence intervals (CI). The analysis of pharmacokinetics will involve subjects included in the primary analysis

set. Estimation of the effect of ethnicity will be performed at each dose level in the study. Graphical methods will be widely used in support of estimation of effects and summary statistics where indicated below. Differences in gender will be addressed descriptively by comparing the PK parameters across gender within an ethnic group.

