6.4 Methods of statistical analyses

6.4.1 Pharmacokinetics

6.4.1.1 Primary analysis

The primary analysis of AZD6140 AUC will be based on log-transformed data using an ANOVA model with effects for dose, weight and ethnicity and subject within ethnicity as a random effect. The primary model will contain only the terms mentioned above. A model including a dose by ethnicity interaction term will also be explored and a term for gender may also be added depending on gender balance. The effect will be estimated using geometric means and two-sided 90% CIs for the ratio of AUC (Japanese/Caucasians) for each dose will

be estimated based on the primary model. The primary contrast will be between Japanese and Caucasians for each dose level. Because there are 2 dosing sequences (AZD6140 50 mg, 200 mg, 400 mg and AZD6140 100 mg, 300 mg, 600 mg) there will be two models of form similar to that described above one for each set of doses. Geometric mean AZD6140 plasma concentrations versus time by dose and ethnic group will be presented graphically. Individual plasma concentrations versus time by dose will be presented graphically. Adjustment for BMI may also be considered by including them as terms in the model. Individual profiles of AUC versus dose will be presented graphically. Dose normalized AUC versus dose and ethnic group will be presented graphically. Adjustment for BMI or weight may also be considered by including them as terms in the model. In the event that there are less than 6 subjects with estimated AUC, $AUC_{(0-t)}$ will replace AUC as one of the primary endpoints. $AUC_{(0-t)}$ and C_{max} will be analyzed in a manner similar to that mentioned above.

AZD6140 plasma concentrations, AUC, $AUC_{(0-t)}$, C_{max} , t_{max} , $t_{1/2}$, CL/F and Vz/F will also be summarized by dose using descriptive statistics detailed in the Statistical Analysis Plan.

Assumptions of normality of the log-transformed AUC, $AUC_{(0-t)}$, and C_{max} data will be explored in the primary analysis and, if necessary an appropriate non-parametric technique will be used to validate the results of the primary analysis.

AR-C124910XX AUC, $AUC_{(0-t)}$, t_{max} , $t_{1/2}$ and C_{max} will be analyzed in a manner similar to AZD6140.

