6.4.4 PK/PD relationships

The relationship between AZD6140, AR-C124910XX, total (AZD6140 + AR-C124910XX) concentrations and %PAI will be investigated using an E_{\max} model. Data from all doses within an ethnic group will be modeled simultaneously regardless of cohort. Observed and predicted %PAI versus exposure will also be presented graphically. The E_{\max} model is a non-linear model of the following form.

$$\% PAI = \frac{E_{\max} C^{\gamma}}{C^{\gamma} + EC_{50}^{\gamma}}$$

Models with sigmoidicity factor γ equal to 1 and where γ is estimated from the data will be explored. A model including a term for ethnicity will be used to explore the effect of ethnicity on model parameters.

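### The primary PK model has no dose-by-ethnicity term and is fitted separately by cohort, so it gives neither dose-specific ethnic ratios nor one ratio over the dose range

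*Protocol*

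**What the plan says.** Section 6.1 of the protocol gives the aim of the PK analysis in two parts. It is to "estimate the effect of ethnicity (Japanese vs. Caucasian) on exposure to AZD6140 and AR-C124910XX over the current dose range" of AZD6140, and a later sentence adds: "Estimation of the effect of ethnicity will be performed at each dose level in the study". No formal hypothesis test is planned; the ratio is reported with a two-sided 90% CI.

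Section 6.4.1.1 fixes the primary analysis of log AUC as an "ANOVA model with effects for dose, weight and ethnicity and subject within ethnicity as a random effect". It then closes the list of terms: "The primary model will contain only the terms mentioned above". A dose-by-ethnicity term is only to be explored in a further model. The ratio and its CI for each dose are nevertheless to come from the primary model, and "The primary contrast will be between Japanese and Caucasians for each dose level". Because Cohort A receives 50, 200 and 400 mg and Cohort B receives 100, 300 and 600 mg, "there will be two models of form similar to that described above one for each set of doses". AUC(0-t) and Cmax are to be handled in a similar way.

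Section 6.5 plans precision for one dose (100 mg) in one cohort, with 6 evaluable subjects per ethnic group out of 8 randomized to active drug. For the PK/PD model, section 6.4.4 takes the other route: "Data from all doses within an ethnic group will be modeled simultaneously regardless of cohort".

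**The concern.** The contrast and the model do not match. With ethnicity as a main effect only, the fitted log difference between Japanese and Caucasian subjects is one coefficient, whatever the dose. The three per-dose ratios and intervals reported for a cohort would be one number and one interval printed three times, and a reader would take them as three separate findings of similar ethnic effect.

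The split adds a second mismatch. The doses interleave, so the two models force the ratio to be equal at 200 and 400 mg but leave it free to differ at 300 mg, which lies between them. If the ratio is taken as constant, nothing in the protocol explains why it should be estimated twice from half the data. If it is allowed to vary by dose, the interaction term is missing. Of the two aims in section 6.1, the primary analysis meets neither.

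**Working it through.** **What the model can estimate.** For subject *i* at dose *d* within one cohort, the primary model is log AUC = dose effect(*d*) + b × weight + g × Japanese + subject effect + error. The Japanese minus Caucasian contrast at dose *d* is g for every *d*. Two cohort fits give g(A) and g(B): two ratios for six doses.

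**Inputs** (sections 6.1 and 6.5): CV 21% for AUC and 20% for Cmax; 90% two-sided CI; 6 evaluable (8 randomized to active) per ethnic group per cohort; two cohorts.

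**The plan's own figure.** Half-width on the log scale = t(0.95, 2n−2) × SD × √(2/n), with the CV used as the log SD, n = 6 and 10 df:
- AUC: 1.8125 × 0.21 × √(2/6) = 0.2197; stated 0.2186.
- Cmax: 1.8125 × 0.20 × √(2/6) = 0.2093; stated 0.2092.

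With SD = √ln(1+CV²) the results are 0.2174 and 0.2072. Section 6.5 therefore reproduces to within 1%.

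**Common ratio for AUC: one cohort (n per group) against both cohorts (2n per group).**

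| Evaluable per cell | One cohort | 90% CI around 1 | Both cohorts | 90% CI around 1 | Narrowing |
|---|---|---|---|---|---|
| 6 | 1.8125 × 0.21 × √(2/6) = 0.2197 (10 df) | (0.80, 1.25) | 1.7171 × 0.21 × √(2/12) = 0.1472 (22 df) | (0.86, 1.16) | 33% |
| 8 | 1.7613 × 0.21 × √(2/8) = 0.1849 (14 df) | (0.83, 1.20) | 1.6973 × 0.21 × √(2/16) = 0.1260 (30 df) | (0.88, 1.13) | 32% |

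Spending one df on weight with 6 per cell gives 0.2223 (9 df) against 0.1475 (21 df). Charging the pooled fit a further df for cohort gives 0.148 (20 df) against 0.222. The narrowing stays near one third. Most of it is 1/√2 from doubling the subjects; the rest is the smaller t quantile.

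**Effect of averaging three doses.** These widths use the single-dose SD. Averaging three doses per subject multiplies the SD by √((1+2ρ)/3), where ρ is the within-subject correlation between doses. The documents do not give ρ. For ρ = 0.5, 0.7 and 0.9 the factor is 0.816, 0.894 and 0.966. With 6 per cell the half-widths then run from 0.179 to 0.212 for one cohort and from 0.120 to 0.142 for both. The factor is common to both options, so the relative narrowing does not change.

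**Dose-specific ratios (interaction in the model).** No dose is given in both cohorts, so pooling adds no subject at any dose; only the error df rise.
- 6 per cell: 1 − t(20 df)/t(10 df) = 1 − 1.7247/1.8125 = 4.8%. With a df for weight: 1 − 1.7291/1.8331 = 5.7%.
- 8 per cell: 1 − 1.7011/1.7613 = 3.4%. With a df for weight: 1 − 1.7033/1.7709 = 3.8%.

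**Whether two sequences force a split.** They do not. One mixed model with a six-level dose factor and a random subject effect accommodates subjects who each receive three of the six doses. Because each dose belongs to one cohort, the dose factor also absorbs any overall cohort difference, and the ethnic comparison stays within cohort.

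**The case against.** A reader might infer that one ratio over the dose range is the protocol's goal and that the split therefore costs a third of the planned precision. The documents do not support that. Section 6.1 also asks for estimation at each dose level, section 6.4.1.1 makes the per-dose contrast primary, and section 6.5 sizes the study for one dose in one cohort. The interval planned there for AUC, (0.80, 1.24), is essentially what a cohort model delivers. With no hypothesis test, no power is lost. For true per-dose ratios, pooling is worth only about 3% to 6%. All of this stands, and it limits the size of the point.

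Keeping the cohorts apart is also a defensible caution. Under section 3.4.2 subjects are assigned to cohorts by the site at screening, and Cohort B starts after Cohort A. Section 1.2 says that ethnic differences have not been investigated, so a constant ratio is an assumption. The two cohort estimates are independent, and combining them by inverse variance would recover most of the pooled precision. These points also stand, but the protocol plans no such combination, and neither argument explains how a model without an interaction can supply different ratios by dose.

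The PK/PD model in section 6.4.4 shows only that pooling was acceptable for another purpose; it does not oblige the ethnic comparison to pool. The dose-proportionality model in section 6.4.1.2 is fitted per ethnic group without mention of cohort, which is weaker still.

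It is also tempting to add that weight probably differs between the ethnic groups, so that estimating its slope twice does harm. The protocol gives no weight data by group, and section 3.3.2 applies the same BMI and weight limits to both.

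**Conclusion.** The defect is the mismatch. Section 6.4.1.1 names a per-dose primary contrast but fixes a model that returns the same ratio at every dose within a cohort, and it fits that model twice on half the subjects. The result is two ratios that serve neither the dose-range aim nor the dose-level aim of section 6.1.

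For a common ratio, analysing the cohorts together narrows the AUC 90% CI by about a third on the log scale with 6 or 8 evaluable per cell. For dose-specific ratios the gain is about 3% to 6%, and the real correction there is the missing interaction.

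The figures assume equal variance in the two cohorts, the plan's CV as the log-scale SD, equal cell sizes and a between-subject comparison. The one-third gain further assumes one ethnic ratio across doses and cohorts. The change should be made, but as an inexpensive improvement: the precision planned in section 6.5 is not lost under the present text.

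**What to change.** Amend section 6.4.1.1, and carry the change into the SAP:

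1. Fit one mixed model to all six doses from both cohorts: log AUC, and separately log Cmax, on dose (six levels), weight and ethnicity, with subject within ethnicity random. Report the overall Japanese/Caucasian ratio with its two-sided 90% CI.
2. Take the per-dose ratios and their 90% CIs from the same model with dose-by-ethnicity added, and state that this version supplies the per-dose contrast.
3. Keep the two cohort-specific fits as a check.

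The cost is analysis wording only; no subjects, samples or visits are added. The downside is that the overall ratio relies on a common ethnic ratio across doses and cohorts and on a common residual variance and weight slope. The interaction model and the cohort fits allow these to be examined, though with 6 to 8 subjects per cell they would detect only large departures, so the assumption should be stated beside the overall ratio.

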6.4.1.2 AZD6140 dose proportionality

Dose proportionality will be assessed using C_{max} and AUC [or $AUC_{(0-t)}$] of AZD6140 as a response variable. The following model will be fit to each ethnic group:

$$AUC = \alpha(dose)^\beta \varepsilon$$

This model will be fit using log-transformed AUC (and C_{max} separately) and dose data based on an ANOVA model with an effect for log-transformed dose and subject as a random effect. A two-sided 90% CI for β will be constructed.

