To assess and compare the pharmacodynamics following single ascending oral doses of AZD6140 in healthy Japanese and Caucasian subjects by assessment of platelet aggregation inhibition and bleeding time.

Study design

This is a randomized, double-blind, placebo-controlled study designed to assess the safety, tolerability, pharmacokinetics and pharmacodynamics of single ascending oral doses of AZD6140 in 20 healthy Japanese and 20 healthy Caucasian male and female (non-childbearing potential) subjects.

Investigational product, dosage and mode of administration

The following study drug will be supplied:

- AZD6140 Immediate release tablets 50 mg, 100 mg and 200 mg
- AZD6140 Placebo to match 50 mg, 100 mg and 200 mg

AZD6140/placebo tablets will be administered as a single dose of 50 mg, 100 mg, 200 mg, 300 mg, 400 mg and 600 mg.

Duration of treatment

Subjects in each ethnic group will be divided into 2 cohorts of 10 subjects each. Within each cohort, 8 subjects will receive single ascending doses of AZD6140 on 3 occasions (Cohort A: 50, 200 and 400 mg; Cohort B: 100, 300 and 600 mg). Two subjects in each cohort will receive placebo on 3 occasions. Consecutive single dose administrations will be separated by a washout period of at least 5 days. Progression to the next dose level will not be permitted until all safety data have been reviewed by the Principal Investigator and study team physician of AstraZeneca. Caucasians subjects may be escalated independently of the Japanese subjects.

Outcome variables

Safety and Tolerability

Safety and tolerability will be assessed by means of incidence and severity of adverse events, 12-lead ECG, vital signs, laboratory parameters and physical examinations.

Pharmacokinetics

Blood samples will be analyzed to determine the plasma concentrations of AZD6140 and its active metabolite, AR-C124910XX. The pharmacokinetic parameters C_{max} , t_{max} , AUC, AUC_{0-t} and $t_{1/2}$, for AZD6140 and AR-C124910XX, and CL/F and V_z/F for AZD6140 will be estimated.

Pharmacodynamics

The level of platelet aggregation inhibition will be evaluated by optical aggregometry (20 μ mol ADP), and bleeding time will be measured.

Pharmacokinetic/Pharmacodynamic Relationship

The relationship between plasma concentrations of AZD6140 and AR-C124910XX and platelet aggregation inhibition measured by optical aggregometry will be determined.

Pharmacogenetics

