	APPENDIX B ADDITIONAL SAFETY INFORMATION	59
	APPENDIX C INSTRUCTIONS FOR BLEEDING TIME EVALUATIONS	63
	APPENDIX D INSTRUCTIONS FOR COLLECTION, STORAGE AND TRANSPORT OF BLOOD SAMPLES FOR GENETIC ANALYSIS.....	65

LIST OF TABLES	PAGE
Table 1 Study plan.....	21
Table 2 Schedule of PK blood sampling	37
Table 3 Schedule of ADP induced platelet aggregation sampling.....	38
Table 4 Schedule of bleeding time sampling.....	39
Table 5 Volume of blood to be drawn from each subject	45

LIST OF FIGURES	PAGE
Figure 1 Study flow chart.....	20

LIST OF ABBREVIATIONS

The following abbreviations are used in this study protocol.

Abbreviation	Explanation
%PAI	Percent inhibition of ADP-induced platelet aggregation
ADP	Adenosine diphosphate
AE	Adverse event
ALT	Alanine aminotransferase
ANOVA	Analysis of variance
APTT	Activated partial prothrombin time
AST	Aspartate aminotransferase
AUC	Area under the plasma concentration curve from zero to infinity
AUC _(0-t)	Area under plasma concentration-time curve from zero to last measurable concentration
bid	Twice a day
BMI	Body mass index
CL	Total body clearance
CL/F	Apparent oral clearance
C _{max}	Maximum plasma drug concentration
CRC	Clinical Research Center
CRF	Case report form
DCF	Data clarification form
EC50	Concentration at which 50% of maximum effect is reached
ECG	Electrocardiogram
EDTA	Ethylene diamine tetra-acetic acid
E _{max}	Maximum effect
F	Fraction of dose systemically available
GCP	Good Clinical Practice
GGT	Gamma glutamyltransferase
ICH	International Conference on Harmonization
IEC	Independent Ethics Committee
IRB	Institutional Review Board
OAE	Other significant adverse event (See Appendix E)

Abbreviation	Explanation
PA _{BL}	Mean response at pre-dose baseline
PA _T	Mean response at time “T”
PD	Pharmacodynamic
PK	Pharmacokinetic
qd	Every day
RBC	Red blood cell
SAE	Serious adverse event
t _{max}	Time to reach peak or maximum concentration or maximum response following drug administration [time]
t _½	Half-life
V _Z /F	Terminal phase volume of distribution
WBC	White blood cell

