6.2.2 Pharmacokinetics

Plasma concentrations of AZD6140 and its metabolite AR-C124910XX will be listed and depicted graphically as a function of time after each single dose administration. PK parameters C_{\max} , t_{\max} , $t_{1/2}$, AUC_(0-t) and AUC for AZD6140 and AR-C124910XX, and CL/F and V_z/F for AZD6140 will be estimated by non-compartmental analysis. AZD6140 and AR-C124910XX C_{\max} will be estimated as the highest measured concentration and t_{\max} will be the time to maximum concentration after single dose administration. The terminal elimination rate constant (λ_z) will be calculated by log-linear regression of the terminal portion of the concentration-time profile. The terminal elimination half-life ($t_{1/2}$) will be calculated as $0.693/\lambda_z$. AUC will be calculated using the linear trapezoidal method up to the last measurable concentration (AUC_{0-t}) and thereafter by extrapolation of the terminal elimination phase to infinity. AZD6140 CL/F will be estimated as the ratio of AZD6140 dose and AUC. The terminal phase volume of distribution, V_z/F , of AZD6140 will be estimated as the ratio of AZD6140 CL/F to λ . The PK parameters for each dose will be summarized by ethnic group - Japanese and Caucasian.

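### If the AUC(0-t) fallback for dose proportionality is used, low doses may be integrated over a shorter time than high doses, which can push the AUC slope β above 1 for a proportional drug

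*Protocol*

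**What the plan says.** Section 6.4.1.2 opens "Dose proportionality will be assessed using C_{max} and AUC [or", with AUC(0-t) as the bracketed alternative. The power model is fitted on the log scale, separately in each ethnic group, with "an effect for log-transformed dose and subject as a random effect". The planned output is the slope: "A two-sided 90% CI for β will be constructed".

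The list of abbreviations defines AUC(0-t) as "Area under plasma concentration-time curve from zero to last measurable concentration". Section 6.2.2 computes it the same way: "AUC will be calculated using the linear trapezoidal method up to the last measurable concentration". The switch is described in section 6.4.1.1: "In the event that there are less than 6 subjects with estimated AUC", AUC(0-t) takes the place of AUC. Section 6.4.1.2 does not repeat that rule, but the bracket reads naturally as the same fallback.

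The doses are "Cohort A: 50, 200 and 400 mg; Cohort B: 100, 300 and 600 mg". Table 2 gives one sampling schedule for every dose, ending at 72 h. No section fixes a common end time for AUC(0-t) or cautions about reading β from it.

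**The concern.** A power model attributes every change in the response across doses to dose. That is fair only if the response measures the same thing at each dose. AUC(0-t) need not do so, because its upper limit is set by the assay. The assay has one lower limit, while concentrations at 600 mg are 12 times those at 50 mg if the drug is proportional. If concentrations fall to the limit before 72 h, they do so earlier at 50 mg, and the low doses lose a larger share of their area. The lost area then appears as exposure that rises faster than dose.

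At stake is the AUC slope in each ethnic group. Section 1.2 reports linear single-dose pharmacokinetics from 30 to 400 mg and says the drug has not yet been given to Japanese subjects. A truncation artefact could therefore be read as a new non-linearity in the first Japanese data. The choice is not a detail left to the SAP, because the protocol itself names the substitute response.

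**Working it through.** The protocol states no figure for β, so there is nothing to reproduce. The check asks what slope AUC(0-t) returns when true β is exactly 1.

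**Inputs from the protocol**
- Six doses in two cohorts (synopsis).
- Sampling at pre-dose, 0.5, 1, 2, 3, 4, 6, 8, 12, 18, 24, 36, 48 and 72 h (Table 2).
- Half-life 6 to 13 h, and Cmax reached within 2 to 4 h (section 1.1).
- Linear trapezoid (section 6.2.2).

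**Assumptions**
- One-compartment oral model with ka 0.8 to 1.0/h, which puts the peak at about 2.4 to 3.6 h.
- Half-lives of 6, 8.5 and 13 h.
- Assay limit expressed as a share of the 50 mg Cmax, since the protocol gives no limit.

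**Formulae**
- C(t) = dose × ka/(ka − ke) × [exp(−ke·t) − exp(−ka·t)], up to a constant, with ke = ln 2 / half-life.
- AUC(0-t) is the trapezoid to the last scheduled sample at or above the limit.
- AUC adds C(last)/ke.
- β is the slope of log AUC(0-t) on log dose, pooled within subjects over both cohorts.

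**One case in full** (half-life 13 h, ka 0.8/h, limit 20% of the 50 mg Cmax)

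| Dose (mg) | Last measurable time (h) | AUC(0-t)/AUC |
|---|---|---|
| 50 | 24 | 0.702 |
| 100 | 48 | 0.918 |
| 200 | 48 | 0.918 |
| 300 | 48 | 0.918 |
| 400 | 72 | 0.977 |
| 600 | 72 | 0.977 |

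Centred log doses are −1.155, 0.231, 0.924 (50, 200, 400 mg) and −0.963, 0.135, 0.828 (100, 300, 600 mg). Their sum of squares is 2.242 + 1.632 = 3.874. The cross-products with the logs of the last column sum to 0.367 + 0.052 = 0.419. The slope of the log share is 0.419/3.874 = 0.108. The slope from AUC itself is 1.006 here, a small trapezoid effect, so β = 1.006 + 0.108 = 1.114.

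**All cases**

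| Assay limit, share of 50 mg Cmax | β from AUC(0-t), true β = 1 |
|---|---|
| 1% to 2% | 1.00 to 1.01 |
| 5% | 1.01 to 1.04 |
| 10% | 1.04 to 1.06 |
| 20% | 1.06 to 1.13 |

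The shift is never downward. It is exactly zero when all six doses end at the same sample, for example half-life 13 h with a limit up to 2%. The slope from AUC to infinity stays between 1.000 and 1.006 throughout. Wherever the extrapolated part at 50 mg exceeds about 25% of AUC, β from AUC(0-t) is at least 1.10.

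**Effect on the interval.** A simulation used 8 active subjects per cohort in one ethnic group and half-life 8.5 h with 20% CV. It took between-subject CV as 21% and within-subject CV as 12% (the latter assumed). The nominal 90% CI covered the true β = 1 in about 69% of trials at a 5% limit, 32% at 10%, and under 5% at 20%.

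**The case against.** The strongest reply is that the harm is doubly conditional: the fallback must be triggered, and the assay must lose the low doses early. In the model above, the 50 mg profile keeps 5 to 9 measurable samples after the peak at limits of 1% to 20%, so a terminal slope could be estimated, AUC would be used, and β would be right. The check does not model the trigger, which could also be met through missing samples unrelated to dose. The document leans towards a sensitive assay too. Section 1.2 reports linearity from 30 mg, below the lowest dose here, and section 3.2 expects concentrations high enough for accurate estimation. All of this stands, and it limits the point to a conditional one.

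It does not remove the point. If concentrations are as high as expected, the fallback is not needed. When it is needed, an obvious reason is a terminal phase that cannot be characterised reliably at low doses, and that is where the truncated share is largest.

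Three stronger readings are not supported:
- A reader might infer that the interval always lengthens with dose and β must exceed 1. The common 72 h window rules that out.
- A reader might take the AUC slope as the only planned evidence on proportionality. Section 6.4.1.2 also fits Cmax, which truncation does not touch. Section 6.4.1.1 plans plots of dose-normalised AUC and summaries of both AUC and AUC(0-t) by dose.
- A reader might judge the bias against an 80-125% tolerance, which over 12-fold is ln 1.25/ln 12 = 0.090. The protocol sets no such limit, and dose proportionality is not among its listed objectives.

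**Conclusion.** The point holds as a conditional one. If AUC(0-t) replaces AUC in the power model and the last measurable time differs between doses, β for a proportional drug is biased upward. The excess is about 0.01 or less with an assay limit up to 2% of the 50 mg Cmax, about 0.04 to 0.06 at 10%, and about 0.06 to 0.13 at 20%. It is zero when all doses are measurable to the same sample. These sizes rest on a one-compartment model, half-life 6 to 13 h, ka 0.8 to 1.0/h and an assumed assay limit. The documents do not show which part of the range applies, nor that the fallback will be used. The direction and mechanism do not depend on those assumptions. This affects a supporting analysis and not the safety objective, but it is worth correcting because the remedy is cheap.

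**What to change.** In section 6.4.1.2, replace the bracketed AUC(0-t) by a partial AUC over one fixed scheduled interval, the same for all six doses and both ethnic groups. Choose the interval before unblinding, for example 0 to 24 h if AZD6140 is measurable to then in nearly all evaluable subjects at the lowest dose. The end time should not be set by the single worst subject, which could shorten it too far. Keep AUC(0-t) as a descriptive parameter, and report the last measurable time by dose beside β.

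The cost is one extra non-compartmental parameter from samples already taken and one or two sentences of text. The downside is that a partial AUC describes less of the total exposure. In the model above with ka 0.8/h, the area to 24 h is about 0.93 of AUC at a half-life of 6 h and about 0.70 at 13 h. The report should say that β then refers to exposure over that interval.
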